Population:	Participants with Kaposi sarcoma (KS), with or without Human Immunodeficiency Virus (HIV) seropositivity
Regimen:	sEphB4-human serum albumin (HSA) will be administered via intravenous infusion. Each cycle of sEphB4-HSA will be 28 days (4 weeks). Each cycle of the study drug includes administration of 2 doses of sEphB4-HSA at 10 mg/kg I.V. administered on Days 1 and 15.
Duration:	
Participants may continue on study protocol as long as their Kaposi Sarcoma (KS) is continuing to respond or is clinically stable on study medication for up to 12 treatment cycles. If complete response (CR) is achieved, the participant will receive one cycle beyond CR. Treatment may be resumed if KS progresses off treatment after a CR. The participant will resume the previous dose that he/she was receiving when CR was achieved. Participants who achieve partial response (PR) or stable disease (SD) may continue the treatment at the dose he/she was receiving when PR or SD was achieved, for a maximum of 12 cycles, if the participant and treating physician feel that it is beneficial to continue treatment. Treatment will be discontinued if the participant experiences unacceptable toxicity or develops one of the protocol-defined reasons for treatment discontinuation. Participants who have partial response or better will be followed up every three months for up to one year, or until an earlier time of disease progression requiring additional treatment.
 
All participants will be followed for 4 weeks after completion of study, removal from study treatment, or until death, whichever occurs first. Participants removed from study treatment for unacceptable adverse event(s) (AE) will be followed until resolution or stabilization of the AE. Participants who withdraw for toxicity reasons should be followed until the toxicity resolves/returns to baseline, or for 4 weeks, whichever is later. In addition, participants who go off study for reasons other than toxicity should be followed for at least 4 weeks after discontinuing drug.

- Primary Objective:** Evaluate the clinical response and toxicity of sEphB4-HSA (at initial dosing of 10 mg/kg every 2 weeks) in participants with KS.
- Secondary Objectives:**
1. Assess the safety of sEphB4-HSA in participants with KS.
 2. Determine trough level exposure of sEphB4-HSA and correlate with tumor response.
 3. Characterize the pharmacodynamics of sEphB4-HSA and correlate these effects with clinical response:
 - i. Effects on viral replication and gene expression of HHV-8.
 - ii. Changes in VEGF-Notch-EphrinB2 angiogenic pathway.
 - iii. Effects on immune response and modulation.
 - iv. Effects on tumor cell apoptosis and proliferation.
 - v. Effect of sEphB4-HSA on HIV plasma viral loads in participants with HIV.
 4. Archive peripheral blood mononuclear cells (PBMCs) and tissue samples to be used in conjunction with samples collected in subsequent trials of sEphB4-HSA for future studies including identification of biomarkers predictive of response.
- Exploratory Objective:** Describe baseline quality of life (QOL) scores, using the functional assessment of HIV Infection (FAHI) + Kaposi sarcoma (KS) questionnaire, in participants with KS, and explore changes in QOL of participants on treatment with sEphB4-HSA.

[figure not shown]
LIST OF ABBREVIATIONS

Ab	Antibody
AB	Associate Basic
ACD	Acid Citrate Dextrose
ACSR	AIDS And Cancer Specimen Resource
ACTG	Aids Clinical Trials Group
AE	Adverse Event
AIDS	Acquired Immunodeficiency Syndrome
ALT	Alanine Aminotransferase
AMC	Aids Malignancy Consortium
AML	Acute Myelocytic Leukemia
ANC	Absolute Neutrophil Count
AST	Aspartate Aminotransferase
AUC	Area Under Curve
BP	Blood Pressure
CBC	Complete Blood Count
CDUS	Clinical Data Update System
CHO	Chinese Hamster Ovary
CI	Clinical Investigator
COPD	Chronic Obstructive Pulmonary Disease
CR	Complete Response
CRF	Case Report Form
CTCAE	Common Terminology Criteria for Adverse Events
CTEP	Cancer Therapy Evaluation Program
CTMB	Clinical Trials Monitoring Branch
CTSU	Cancer Trials Support Unit
DARF	Drug Accountability Record Form
DBP	Diastolic Blood Pressure
DHHS	Department Of Health and Human Services
DLT	Dose limiting toxicity
DMU	Data Mapping Utility

DSMB	Data And Safety Monitoring Board
DSMP	Data And Safety Monitoring Plan
DTL	Delegation of Tasks Log
ECOG	Eastern Cooperative Oncology Group
EKG	Electrocardiogram
ELISA	Enzyme-Linked Immunosorbent Assay
ELISPOT	Enzyme-Linked Immunosorbent Spot
FAHI	Functional Assessment of HIV
FCBP	Females of Childbearing Potential
FDA	Food and Drug Administration
FAHI	Functional Assessment of Human Immunodeficiency Virus Infection
HAART	Highly Active Antiretroviral Therapy
HIV	Human Immunodeficiency Virus
HSA	Human Serum Albumin
HUVEC	Human Umbilical Vein Endothelial Cells
IAM	Identity and Access Management
IDB	Investigational Drug Branch
IL	Interleukin
IME	Important Medical Events
IRB	Institutional Review Board
I.V.	Intravenous
IVR	Investigator
KPS	Karnofsky Performance Score
KS	Kaposi Sarcoma
KSHV	Kaposi Sarcoma Associated Herpes Virus
LANA	Latency-Associated Nuclear Antigen
MDS	Myelodysplastic Syndrome
MSC	Mesenchymal Stem Cells
MTD	Maximum Tolerated Dose
NCI	National Cancer Institute
NRTI	Nucleoside (and Nucleotide) Reverse Transcriptase Inhibitors

NNRTI	Non-Nucleoside Reverse Transcriptase Inhibitors
NPIVR	Non-Physician Investigator
NSAIDs	Non-Steroidal Anti-Inflammatory Drugs
NYHA	New York Heart Association
ODMC	Operations and Data Management Center
OHAM	Office of HIV and AIDS Malignancy
PBMC	Peripheral Blood Mononuclear Cells
PD	Progressive Disease
PI	Principal Investigator
PIO	Protocol Information Office
PMB	Pharmaceutical Management Branch
PR	Partial Response
QOL	Quality of life
RCR	Registration and Credential Repository
RNA	Ribonucleic Acid
RTK	Receptor Tyrosine Kinase
SAE	Serious Adverse Event
SBP	Systolic Blood Pressure
SD	Stable Disease
SGOT	Serum Glutamic-Oxaloacetic Transaminase
SGPT	Serum Glutamic Pyruvic Transaminase
SOC	System Organ Class
SOP	Standard Operating Procedure
SPEER	Specific Protocol Exceptions to Expedited Reporting
SUSAR	Serious and Unexpected Suspected Adverse Drug Reaction
SWG	Scientific Working Group
TORO	Transfer of Regulatory Obligations
ULN	Upper Limit of Normal
VEGF	Vascular Endothelial Growth Factor
VEGFR	VEGF Receptors
WBC	White Blood Cell

PROTOCOL SCHEMA

*If complete response (CR) is achieved, the participant will receive one cycle beyond CR. Treatment may be resumed if KS progresses off treatment after a CR. The participant will resume the previous dose that he/she was receiving when CR was achieved. Participants who achieve PR or stable disease (SD) may continue the treatment at the dose he/she was receiving when PR or SD was achieved, for a maximum of 12 cycles, if the participant and treating physician feel that it is beneficial to continue treatment.

**Assuming at least 4 doses of sEphB4-HSA administered.

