4.3 Duration of Therapy

In the absence of treatment delays due to AE(s), treatment may continue for a maximum of 12 cycles or until one of the following criteria listed in [Section 4.5](#) applies. If CR is achieved, the participant will receive one cycle beyond CR. Treatment may be resumed if KS progresses off treatment after a CR, up to a maximum of 12 cycles. The participant will resume the previous dose that he/she was receiving when CR was achieved. Participants who achieve PR or SD may continue the treatment at the dose he/she was receiving when PR or SD was achieved for a maximum of 12 cycles, if the participant and treating physician feel that it is beneficial to continue treatment.

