4.5 Criteria for Removal from Treatment

Participants will be removed from study treatment when any of the criteria listed in [Section 5.0](#) and below applies. The reason for study treatment removal and the date of the participant's last treatment must be documented in the Off Protocol Treatment Form in Advantage eClinical. The date the participant was removed from study treatment must be documented in the source.

- Uncontrolled sustained hypertension, which will be defined as systolic BP > 140, and diastolic BP > 90, even with use of antihypertensive medications.
- Disease progression after completing 2 or more cycles (or at least after 4 doses of sEphB4-HSA).
- Dose delay of more than 28 days.
- Rapid progression of disease that is deemed to be life-threatening.
- Intercurrent illness that prevents further administration of treatment.
- Any participant who develops Multicentric Castleman's disease or a life-threatening systemic inflammatory syndrome will not receive further sEphB4-HSA and will be managed using the best judgment of the treating physician.
 - **These events require mandatory notification of a study chair within 24 hours which will result in immediate notification of all participating sites and a conference call to assess the safety of continued enrollment.**
- Participants who experience Steven-Johnson Syndrome or major allergic reaction.
- Participants who become pregnant or need to breast-feed.
- Participants who require systemic chemotherapy for the treatment of a malignancy other than KS.
- Participants who are noncompliant with respect to taking drugs, keeping appointments, or having tests required for the evaluation of drug safety and efficacy.
- Participants have the right to withdraw from the study at any time for any reason.

- The Investigator has the right to remove participants from the study for clinical reasons which he/she believes are life-threatening to the participant even if such reasons do not fall into the toxicity classifications discussed in [Section 5.0](#).
- General or specific changes in the participant's condition render the participant unacceptable for further treatment in the judgment of the investigator.
- Unacceptable AE(s).

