9.0 MEASUREMENT OF EFFECT

All participants will be evaluated for response by physical examination on Day 1 of every cycle (± 3 days). See [Appendix I](#) for the KS Tumor Assessment schedule.

CTEP-registered physician investigators and CTEP-registered advanced practice clinicians who are non-physician investigators (i.e., NP or PA) may perform toxicity and response assessment per local licensure requirements.

Evaluable for toxicity:

All participants will be evaluable for toxicity from the time of their first treatment with sEphB4-HSA. For the primary toxicity endpoint, we will report toxicities occurring during the first two cycles of therapy.

Evaluable for objective response:

Only those participants who have measurable disease present at baseline, have received at least two cycles of therapy, and have had their disease re-evaluated will be considered evaluable for response. These participants will have their response classified according to the definitions stated below (Note: Participants who exhibit objective disease progression prior to the end of Cycle 1 will also be considered evaluable.). For the primary efficacy endpoint, we will report the clinical response (CR or PR) rate after 2 or more cycles of treatment. Participants with KS which progress prior to the end of Cycle 2 will be considered to have treatment failure.

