10.0 STATISTICAL CONSIDERATIONS

10.1 Study Design and Endpoint

This is a multi-institutional, Phase II single-agent trial of sEphB4-HSA in participants with KS. Participants will be administered sEphB4-HSA via intravenous infusion. Each cycle of sEphB4-HSA will be 28 days (4 weeks). Each cycle of the study drug includes administration of 2 doses of sEphB4-HSA at 10 mg/kg administered on Days 1 and 15. The primary endpoint simultaneously evaluates clinical response and toxicity after a minimum of 2 cycles of therapy with sEphB4-HSA in participants with KS. Participants may continue on study protocol as long as their KS is continuing to respond or is clinically stable on study medication for up to 12 treatment cycles. If CR is achieved, the participant will receive one cycle beyond CR. Treatment may be resumed if KS progresses off treatment after a CR. The participant will resume the previous dose that he/she was receiving when CR was achieved. Participants who achieve PR or SD may continue the treatment at the dose he/she was receiving when PR or SD was achieved, for a maximum of 12 Cycles, if the participant and treating physician feel that it is beneficial to continue treatment. Treatment will be discontinued if the participant develops unacceptable toxicity or develops one of the protocol-defined reasons for treatment discontinuation. Participants who show PR or better disease will be followed every 3 months for up to 1 year, or until an earlier time of disease progression requiring additional treatment. All participants will be followed for 4 weeks after treatment completion.

All participants who receive any amount of the study drug will be evaluable for toxicity. Toxicities will be tabulated by type and grade, according to dose cohort. Toxicity will be based on CTCAE version 5.0.

Unacceptable toxicities include all of the below which are deemed to be *at least probably* attributed to the study drug:

- Grade 4 hematological toxicity (thrombocytopenia, neutropenia on growth factor) that lasts > 4 weeks
- Steven-Johnson Syndrome
- Major allergic reaction which requires epinephrine
- Grade 4 non-hematological toxicity that does not resolve with optimal supportive care (e.g., fluids, electrolyte replacement, anti-diarrheal and titration of antihypertensive medications)
- Grade 3 neuropathy for at least 4 weeks

Primary endpoint analysis plan

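### Synopsis and 10.1 do not match 4.3 and 4.5 on progression before four doses, and 9.0 and 10.7 leave open whether a participant stopped in that interval is in the response denominator

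*Combined protocol and SAP*

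**What the plan says.** **Continuation.** The synopsis (Duration) states: "Participants may continue on study protocol as long as their Kaposi Sarcoma (KS) is continuing to respond or is clinically stable on study medication". The cap is 12 cycles. Section 10.1 repeats this: "Participants may continue on study protocol as long as their KS is continuing to respond or is clinically stable on study medication". Neither gives a minimum number of doses. Both add that treatment ends if the participant "develops one of the protocol-defined reasons for treatment discontinuation".

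**Removal.** Under 4.3, "treatment may continue for a maximum of 12 cycles or until one of the following criteria listed in" Section 4.5. The progression entry in 4.5 reads: "Disease progression after completing 2 or more cycles (or at least after 4 doses of sEphB4-HSA". The same list allows removal at any time for life-threatening rapid progression, for a change in condition that the investigator judges to rule out further treatment, and on the participant's own withdrawal.

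**Response analysis.** Section 9.0 restricts evaluability to participants with measurable disease at baseline, at least two cycles received and a re-evaluation. Its note adds: "Participants who exhibit objective disease progression prior to the end of Cycle 1 will also be considered evaluable". The same paragraph then classes progression before the end of Cycle 2 as treatment failure. Section 10.7 puts all eligible participants in the main response analysis (with a possible exception for those never dosed), counts progressive disease as failure, and rests all conclusions on that set.

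**Toxicity analysis.** Section 9.0 takes the first two cycles as the primary toxicity window. Anyone who received study drug is evaluable (9.0, 10.1, 10.6).

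**The concern.** Tumor assessment is due on Day 1 of every cycle, so progression can be recorded at Cycle 2 Day 1 after two doses. At that visit the condition in the synopsis and 10.1 is no longer met, while the progression criterion in 4.5 has not been reached. Sites in a multi-institutional trial could handle the same finding differently.

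The choice can reach the primary endpoint in two ways. A participant who is stopped has not received two cycles and may fall outside 9.0's evaluable set, although certain not to be a responder at that point; one who goes on to complete two cycles is evaluable. The stopped participant also stays in the toxicity denominator with fewer doses than the two-cycle window assumes.

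**Working it through.** **1. The plan's own figures.** Inputs from 10.2: n = 20; success needs at least 9 responders and at most 3 participants with unacceptable toxicity; null rates 0.30 and 0.30; alternative rates 0.60 (response) and 0.10 (toxicity). Exact binomial, response and toxicity taken as independent:
- Power = P(X ≥ 9 | 20, 0.60) × P(T ≤ 3 | 20, 0.10) = 0.9435 × 0.8670 = 0.818 (stated 0.82).
- Significance level = the larger of P(X ≥ 9 | 20, 0.30) = 0.113 and P(T ≤ 3 | 20, 0.30) = 0.107, so 0.113 (stated 0.11).

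Both reproduce. The conflict does not alter them as design figures.

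**2. Who falls in the gap.** Cycle 1 ends on Day 28 and Cycle 2 Day 1 is Day 29. Section 9.0 allows the exam ±3 days, so Days 26-32. Progression found on Days 26-28 is inside the 9.0 exception. Progression found on Day 29 or later is outside it, but still before the end of Cycle 2. If that participant is stopped:

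| Rule | Status |
|---|---|
| 9.0, two-cycle requirement with its note | not evaluable |
| 9.0, failure sentence | treatment failure |
| 10.7 | in the main analysis, failure |

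**3. Response proportion.** The documents give no early-progression rate, so the number dropped, k, is assumed. With 9 responders the reported rate is 9/(20 − k):
- k = 0: 9/20 = 45%
- k = 1: 9/19 = 47%
- k = 2: 9/18 = 50%
- k = 3: 9/17 = 53%
- k = 4: 9/16 = 56%

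The decision rule is a count. Removing non-responders from a fixed 20 leaves the number of responders unchanged, so P(at least 9) stays at 0.113 for a true rate of 0.30. Under 10.7 the denominator stays at 20 and the proportion does not move either.

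**4. Toxicity.** Assumptions: constant risk per dose, a true rate of 0.30 over four doses, and a fraction f of participants stopped after two doses.
- Risk over two doses = 1 − √(1 − 0.30) = 0.163.
- Average risk = (1 − f) × 0.30 + f × 0.163: 0.286 at f = 0.10 and 0.273 at f = 0.20.
- P(T ≤ 3 | 20) = 0.133 and 0.164, against 0.107 with full dosing.

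These values are for the toxicity part alone. Multiplied by P(X ≥ 9 | 20, 0.60) = 0.943, assuming independence, the joint probability goes from 0.101 to 0.125-0.154.

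**The case against.** - **The synopsis and 10.1 are permissive and defer to the stopping list.** They say participants may continue, and they point to protocol-defined reasons, which 4.5 lists and 4.3 invokes. This weakens the conflict without removing it: continuation is conditioned on response or stability, and the list does not cover ordinary progression after two doses.
- **A reader might infer that 4.5 keeps early progressors on drug.** It does not. It only omits early ordinary progression as a removal reason, and investigator judgment and withdrawal apply throughout. The schema footnote ("Assuming at least 4 doses of sEphB4-HSA administered") cannot settle the matter, because the diagram it belongs to is not shown.
- **10.7 protects the response analysis.** This is the strongest reply. If 10.7 governs, the participant is a failure whether stopped or dosed. But 9.0 restricts evaluability in the same paragraph that defines the primary efficacy endpoint, 10.2 speaks of 20 evaluable participants, and nothing says which section prevails.
- **A reader might infer that the false-positive risk for response rises.** If dropped participants were replaced, P(at least 9 of 20) at a true rate of 0.30 would go from 0.113 to between 0.153 and 0.317, for 10-20% progressing at that exam and depending on the share of exams affected. No replacement rule is described and 3.3.1 caps enrolment at 20, so the documents do not support that reading.
- **Toxicity follow-up is not cut in half.** Section 8.4 requires a visit 4-6 weeks after Day 28 of the final cycle; after stopping in Cycle 1 that is Days 56-70, which reaches the end of the two-cycle window. What falls is dose exposure. An exam on Days 30-32 may also follow a third dose, which makes the reduction smaller.

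**Conclusion.** The point holds as an inconsistency that should be repaired. The treatment passages give no single answer for ordinary progression before four doses, and 9.0 disagrees with itself and with 10.7 on whether a participant stopped in that interval is evaluable.

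The effect on response is limited to the reported proportion, and only if 9.0's evaluability rule is applied literally: 45% could read as 47% to 56% for 1 to 4 dropped participants. There is no effect under 10.7, and no easier route to 9 responders without replacement.

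The toxicity effect does not depend on 10.7. It is modest and rests on assumptions the documents do not supply: 10-20% stopped after two doses and constant risk per dose. On those, the chance of meeting the toxicity limit at a true rate of 0.30 moves from 0.107 to 0.133-0.164. No view is taken on which stopping rule is right.

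**What to change.** 1. Reconcile the synopsis and 10.1 with 4.3 and 4.5, so that one statement covers progression before two cycles or four doses. Which rule to adopt is for the sponsor.
2. Change the evaluability note in 9.0 so that progression at any time before the end of Cycle 2 is evaluable and counts as treatment failure whatever number of doses was given. This agrees with 9.0's own failure sentence and with 10.7.

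Cost: wording at the next amendment, with no added participants or visits. The reported response rate may be slightly less favourable than under a literal reading of the present 9.0.

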1.0 OBJECTIVES

1.1 Primary Objective

To evaluate the clinical response and toxicity of sEphB4-human serum albumin (HSA) (at initial dosing of 10 mg/kg every 2 weeks) in participants with Kaposi sarcoma.

1.2 Secondary Objectives

1.2.1 To assess the safety of sEphB4-HSA in participants with KS.

1.2.2 To determine trough level exposure of sEphB4-HSA and correlate with tumor response.

1.2.3 To characterize the pharmacodynamics of sEphB4-HSA and correlate these effects with clinical response.

1.2.3.1 Effects on viral replication and gene expression of HHV-8.

1.2.3.2 Changes in VEGF-Notch-EphrinB2 angiogenic pathway.

1.2.3.3 Effects on immune response and modulation.

1.2.3.4 Effects on tumor cell apoptosis and proliferation.

1.2.3.5 Effects on sEphB4-HSA on Human Immunodeficiency Virus (HIV) plasma viral loads in participants with HIV.

1.2.4 To archive peripheral blood mononuclear cells (PBMCs) and tissue samples to be used in conjunction with samples collected in subsequent trials of sEphB4-HSA for future studies including identification of biomarkers predictive of response.

1.3 Exploratory Objective

Describe baseline quality of life (QOL) scores, using the functional assessment of HIV Infection (FAHI) + Kaposi sarcoma (KS) questionnaire, in participants with KS, and explore changes in QOL of participants on treatment with sEphB4-HSA.

2.0 BACKGROUND

2.1 Kaposi Sarcoma

Kaposi sarcoma (KS) is a multifocal angioproliferative disorder of vascular endothelium, most associated with infection with the Kaposi sarcoma associated herpes virus (KSHV), also known as human herpes virus-8 (HHV-8). KS is associated with a number of epidemiologic and pathophysiologic factors. KS is classified into four distinct clinical types: classic Mediterranean KS, African-endemic KS, immunosuppressive drug-related KS, and HIV-related KS. A rare disease before the era of HIV and AIDS, HIV-related KS is the most frequent malignancy in HIV-infected patients.

The pathogenesis of all four types of KS is alike. Initiation of KS starts with HHV-8 infection and transformation of human endothelial cells, eventually forming the neoplastic spindle-cell component of the KS.¹ Viral gene products of HHV-8 affect both cell cycle regulation and the control of apoptosis, and segments of the HHV-8 genome contain viral oncogenes that are important in the pathogenesis of tumor formation.² Like all herpesviruses, HHV-8 alternates between two phases of its life cycle—the latent and lytic phases. Latent and lytic phases of the HHV-8 life cycle are both involved in KS development. During latency, the virus is maintained as episomes attached to the host chromosome, and the virus is replicated with the host chromosome, and subsequently passed to descendant cells.³ Though gene expression is limited during the latent phase, latently expressed viral proteins have been shown to promote tumorigenesis by dysregulating the cellular mechanisms which would normally protect cells from atypical proliferation.⁴ Eventually, this leads to transformation of endothelial-derived spindle cells with hyperproliferation and reactivation of the latent HHV-8 with lytic replication of viral proteins that can promote angiogenesis and activate further inflammation.⁵ Characteristic of the lytic phase is active viral replication and active expression of a wide range of HHV-8-gene products.⁶ Vascular cells that are infected with HHV-8 can lead to transformation of endothelial-derived spindle cells with hyperproliferation and development of characteristic KS lesions.⁵ The microscopic features of all four different types of KS do not differ. All forms show evidence of angiogenesis, inflammation, and spindle cell proliferation.

KS can affect many organs. KS manifests most frequently as a disease of the skin. In many advanced cases, KS involves organs such as the lungs, liver, or gastrointestinal tract.⁷ At this time, KS is incurable. Available therapies are for palliation. Systemic chemotherapy is generally used for patients with more advanced disease or evidence of rapid progression of disease. The major goals of treatment are symptom palliation, prevention of disease progression, and reduction of tumor burden to alleviate lymphedema, organ compromise, and psychological stress. The standard therapies for visceral or advanced cutaneous KS include cytotoxic chemotherapy such as liposomal anthracycline and paclitaxel.⁸ Liposomal doxorubicin has superior efficacy and favorable tolerability and toxicity compared to the combination of non-liposomal doxorubicin, vincristine, and bleomycin with overall response rates of 59% in HIV patients.⁹ In classical KS, response rates to liposomal doxorubicin can be higher.¹⁰ However, CR rates are uncommon and there is no cure. At this point in time, no targeted therapy has been fully developed for KS. Given the role of angiogenesis in KS tumorigenicity, antiangiogenic approaches represent potential therapeutic targets. A novel, effective drug would be welcomed for patients with KS. Given

KS skin lesions are visibly apparent; the disease can often result in significant psychological problems and social stigma for patients with KS. Symptoms of systemic KS include pain, diarrhea, weight loss, edema, and oral sores. In many cases, KS can severely compromise the QOL by causing physical suffering, scarring, and deformity. Lymphedema, particularly in the face, genitalia, and lower extremities are not uncommon and impair functional ability.¹¹ Survival can often be marked by poor QOL, making it difficult for patients to deal with their disease. While the introduction and use of highly active antiretroviral therapy (HAART) therapy has resulted in a steep decline in the incidence of HIV-related KS with improvements in survival, CRs are rare and the disease remains incurable.^{12,13} Therefore, QOL for patients with KS still remains a major issue. Since QOL has been, and continues to be, such a vital issue in KS, QOL measures have been used as endpoints in AIDS-related KS.¹⁴⁻¹⁶ In a phase II trial with low-dose etoposide, responders had a statistically improvement in pain, physical and bodily pain distress compared to non-responders.¹⁵ In an AIDS Malignancy Consortium (AMC) trial of liposomal doxorubicin versus paclitaxel, two common drugs used in advanced KS, the KS Functional Assessment of HIV Infection (FAHI) QOL instrument with three supplemental questions on pain, swelling and physical appearance was used to collect QOL data.^{17,18} This study was able to show that with treatment, there were significant improvements reported between baseline and treatment values of pain and swelling; these values are of clinical value as this was not captured by the given response values (i.e., complete response, partial response). Clinicians currently take QOL improvement into account when treating KS patients with chemotherapy drugs like liposomal doxorubicin and paclitaxel, which have clear side effects. Therefore, it is also important to consider QOL changes when moving a therapy forward into the clinical arena.

[figure not shown]
